- 1) Determine whether immunization with the vaccine generates a humoral response against Tumor Associated Carbohydrate Antigens.
- 2) Determine the delayed-type hypersensitivity (DTH) response to the immunizing mimotope
- 3) Determine the effect of a late booster immunization on the humoral response against TACAs

Exploratory Objective: Determine the effect of immunizing mimotope on circulating tumor cells (CTCs)

Study Population: We plan to consent approximately 24 subjects with hope of reaching our enrollment goal of 18 women, ages 18 and older from the breast cancer clinics (Medical Oncology and Ladies Oncology Clinics) at the Winthrop P. Rockefeller Cancer Institute at the University of Arkansas for Medical Sciences (UAMS) campus.

Inclusion Criteria: Females with histologically or cytologically confirmed stage IV breast cancer (newly diagnosed metastatic or relapsed after primary or adjunctive therapy, which has not required a treatment change for 2 months) will be invited to participate.

Exclusion Criteria: Women who are pregnant, breast-feeding, have autoimmune disease or are immunosuppressed or receiving systemic corticosteroids will be excluded from the study.

Investigational product: P10s-PADRE administered with the MONTANIDE™ ISA 51 VG

Study Design: After signing IRB approved consent, cohorts of 3-6 stage IV breast cancer subjects will be enrolled into the study. The vaccine doses will be prepared and dispensed by the UAMS Pharmacy following the manufacturer's instructions. Subjects will receive up to 2.0 mL subcutaneous (SC) injections of the vaccine on 5 separate occasions during Weeks 1, 2, 3, 7, and 19. The first cohort will begin with the 300 µg dose, and then the subsequent cohorts will escalate to 500 µg or de-escalate to 100 µg as determined by the toxicity criteria shown in Table 1 of Section 7. The immunization at week 19 is considered a booster immunization. The vaccine will be administered at rotating sites on the limbs or abdomen by nurses in the Infusion Center at the Cancer Institute, using a dose volume of up to 2.0 mL per injection. Based on a series of criteria measuring tolerance and immune response in the first cohort on Week 9 (Section 7, Table 1), the P10s-PADRE dose will either be increased to 500 µg/mL or decreased to 100 µg/mL for the second cohort of subjects. The study will last for approximately 12 – 24 months.

3. Background

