- 8) Subjects must have no other current malignancies. Subjects with prior history at any time of any *in situ* cancer, including lobular carcinoma of the breast *in situ*, cervical cancer *in situ*, atypical melanocytic hyperplasia or Clark I melanoma *in situ* or basal or squamous skin cancer are eligible, provided they are disease-free at the time of registration. Subjects with other malignancies are eligible if they have been continuously disease free for \geq 5 years prior to the time of registration.

- 9) Subjects must not have autoimmune disorders or conditions of immunosuppression. This includes, but is not limited to being treated with corticosteroids, including oral steroids (i.e. prednisone, dexamethasone), continuous use of topical steroid creams or ointments or any steroid-containing inhalers. Subjects who have been on systemic steroids will require a 6-week washout period. Subjects who discontinue the use of these classes of medication for at least 6 weeks prior to registration are eligible if, in the judgment of the treating physician, the subject is not likely to require these classes of drugs during the treatment period. Replacement doses of steroids for subjects with adrenal insufficiency are allowed.
- 10) Women of childbearing potential must not be pregnant (negative serum pregnancy test must be done 48 hours prior to receiving the first dose of study drug) or breast-feeding, due to the unknown effects of peptide/mimotope vaccines on a fetus or infant.
- 11) Women of childbearing potential must be counseled to use an accepted and effective method of contraception (including abstinence) while on treatment and for a period of 18 months after completing or discontinuing treatment. Accepted methods include oral contraceptives, barrier method, IUDs, and abstinence.
- 12) Subjects must have obtained a white blood cell (WBC) count $\geq 3,000/\text{mm}^3$ and platelet count $\geq 100,000/\text{mm}^3$ within 2 weeks prior to registration.
- 13) Subjects must have a serum glutamic-oxaloacetic transaminase (SGOT)/aspartate aminotransferase test (AST) and bilirubin $\leq 2 \times$ institutional upper limit (IUL) of normal and serum creatinine $\leq 1.8 \text{ mg/dl}$, all obtained within 2 weeks prior to registration.
- 14) Subjects must be immunocompetent as measured by responsiveness to one recall antigens by skin testing.

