- Toxicity evaluations using the NCI CTCAE (National Cancer Institute Common Terminology Criteria for Adverse Events) Version 4.0. Toxicities to be assessed are the laboratory parameters listed in the study calendar, as well as any sign or symptom found during the history and physical examination not noted at prestudy or on the baseline evaluation. Special attention will be paid to signs and symptoms related to injection reactions, injection site reactions or symptoms or laboratory findings indicating autoimmune toxicities.
- Concomitant medications will be collected from registration to end of treatment.
- Study lab samples. Up to 40 mLs of blood will be collected in red and purple tubes for circulating tumor cell evaluation, TACA (tumor associated carbohydrate antigens) assessment, and immune effector assays.

Week 20

- Complete blood count with differential

Week 21

- Complete medical history and physical examination
- Complete blood count with differential
- Other blood tests include:
 - Collection of serum samples used to measure the immune response to the vaccine. If vaccine is given on these days, the study labs will be drawn before the vaccine is administered.
 - SGOT (Serum glutamic-oxaloacetic transaminase)
 - Alkaline Phosphatase Level
 - LDH (lactate dehydrogenase)

- GGT (gamma-glutamyl transferase)
 - Creatinine
 - Calcium
 - Albumin
 - Amylase
 - TSH (thyroid stimulating hormone)
 - T₄
 - ANA (Anti-nuclear antibody)
 - PT/PTT
 - Bilirubin
- Toxicity evaluations using the NCI CTCAE (National Cancer Institute Common Terminology Criteria for Adverse Events) Version 4.0. Toxicities to be assessed are the laboratory parameters listed in the study calendar, as well as any sign or symptom found during the history and physical examination not noted at prestudy or on the baseline evaluation. Special attention will be paid to signs and symptoms related to injection reactions, injection site reactions or symptoms or laboratory findings indicating autoimmune toxicities.
- Concomitant medications will be collected from registration to end of treatment.
- DTH Skin Test to test the subjects' immunocompetency. Trichophyton Antigen and the Candida antigen will be administered intradermally (id) as control antigens at separate locations on the subject's back, and the resulting induration will be read 48– 72 hours later; 100 µg Mimotope P10s-PADRE will be given id alongside the control antigens to determine subjects' DTH response to vaccine.

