Administration of study vaccine	
Experimental agent may be toxic or harmful.
 
First time use in humans
 
Risk of local reactions (i.e. swelling, redness, tenderness, itching, extravasations)
 
Potential for side effects ranging from hematologic toxicities and hypersensitivity reactions to anaphylaxis
 
Unanticipated risks
 
Unknown risks
	
Careful monitoring by clinic visits and 24 hour, 7 days per week physicians on call for unexpected problems
 
Only non-pregnant, non-lactating females may participate. The use of contraception during the study and the use of contraception for 18 months post completion of the trial are required.
 
Frequent laboratory tests including complete blood count (CBC) with differential, liver function tests, etc.
 
Close and frequent monitoring of subjects by qualified staff
 
DTH assay to monitor for hypersensitivity reactions
 
Emergency equipment including crash carts, advanced cardiac life support (ACLS) certified staff and rescue medications such as Benadryl, epinephrine, high dose steroids, etc. will be on-site during administration.
 
The Medical Monitor will review all toxicities on a regular basis and will be available to aid subjects as needed.
 
The study drug may be discontinued.
 
This research is being conducted at an experienced clinical research center.
 
Reporting and monitoring mechanisms are in place for AEs, serious adverse events (SAEs) and unanticipated problems.

Administration of MONTANIDE™ ISA 51 VG	
Dermatology/Skin: local erythema, rash, pruritis
 
Gastrointestinal: diarrhea, anorexia, nausea, vomiting, abnormal taste
 
Hepatic: elevated
	
Careful monitoring by clinic visits and 24 hour, 7 days per week physicians on call for unexpected problems
 
Only non-pregnant, non-lactating females may participate. The use of contraception during the study and the use of contraception for 18 months post completion of the trial are required.

Procedure	Risks	Measures to Minimize Risks

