or lower. Samples will be kept for maximum of 5 years. At the end of year 5, any unused specimen will be mixed with bleach and disposed in a sink. All specimen containers (tubes and containers) will be disposed into biohazard red plastic bags according to UAMS Occupational Health & Safety's policy. Red bag waste will be picked up by occupational Health & Safety for final disposal.

10. Study Calendar

TEST/EVENT		WEEK ⁷																			
		Prestudy ¹	48 hrs later	48 hours prior to dosing	1	2	3	4	5	48 hrs later	6	7	8	9	48 hrs later	19	20	21	48 hrs later	24	Follow up ¹⁰
Informed Consent		x																			
Vaccination with Mimotope P10s-PADRE/ MONTANIDE™ ISA 51 VG					x ⁹	x ⁹	x ⁹					x ⁹				x ⁹					
Adverse Events					x	x	x					x		x		x		x		x	
Concomitant medications ⁸	x				x	x	x					x		x		x		x		x	
History/Physical Exam/	x				x	x	x					x		x		x		x		x	
CBC with Differential	x				x	x	x	x			x	x	x	x		x	x	x		x	
SGOT	x					x						x		x		x		x		x	
Bilirubin	x					x						x		x		x		x		x	
Alkaline Phosphatase	x					x						x		x		x		x		x	
LDH (lactate dehydrogenase)	x					x						x		x		x		x		x	
GGT (gamma-glutamyl transferase test)	x					x						x		x		x		x		x	
Creatinine	x					x						x		x		x		x		x	
Calcium	x					x						x		x		x		x		x	
Albumin	x					x						x		x		x		x		x	
Amylase	x					x						x		x		x		x		x	
TSH (thyroid stimulating hormone)	x					x						x		x		x		x		x	
T ₄	x					x						x		x		x		x		x	
Anti-nuclear Antibody (ANA)	x					x						x		x		x		x		x	
PT/PTT	x					x						x		x		x		x		x	
Serum Pregnancy Test ²	x			x																	
Study Lab ³	x ⁴				x	x	x					x		x		x		x ⁴		x ⁴	
DTH Skin Test ^{5,6}	x ⁵							x ⁶					x ⁶					x ⁶			
Read DTH Skin Test ^{5,6}		x ⁵							x ⁶					x ⁶				x ⁶			

¹Prestudy is to be completed within 14 days before beginning injections.

²For women of child bearing potential, a serum pregnancy test must be done at prestudy and within 48 hours prior to dosing. One test may suffice for both

³ Study lab samples. Up to 40 mLs of blood will be collected in purple tubes for circulating tumor cell evaluation, TACA (tumor associated carbohydrate antigens) assessment, and immune effector assays. Specimens will be picked up by [name] or a member of his research staff. Call [name] for pick-up.

⁴An additional 6.0 ml of blood will be taken during these study labs (Pre-Study, Week 21, and Week 24) to assay circulating tumor cells (CTCs).

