⁵The DTH skin test at prestudy will test the subjects' immunocompetency. Control antigens, Trichophyton Antigen and Candida antigen, will be administered id and the resulting induration will be ready at 48 - 72 hours post injection.

⁶ The DTH skin tests on weeks 5, 9 and 21 will test the DTH response to Mimotope P10s-PADRE. Trichophyton Antigen and Candida antigen will be administered id alongside Mimotope P10s-PADRE as control antigens to assess immunocompetency. DTH skin test indurations will be read at 48 – 72 hours post injection.

⁷ Visits must occur at set time points mentioned in the study calendar (+/- 3 days) with the exception of reading the skin test which must occur 48-72 hours post administration.

⁸ Concomitant medications will be collected from registration to end of treatment.

⁹ Post vaccine administration, the following vital signs will be monitored every 15 minutes (+/- 5 minutes) for one hour: blood pressure, temperature, and pulse.

¹⁰ Follow up visits shall begin with the next scheduled standard of care appointment and then shall occur every six months for five years and then yearly until death.

11. Criteria for Evaluation

Primary Objective – Safety:

- **Determination of DLT:** See Section 8, “Risks and Toxicities to be Monitored”. Any event that meets the dose limiting criteria will be determined a dose limiting toxicity.

Secondary Objectives – Immune Response:

- **Immunological Evaluation:** Serum will be collected at the Study Lab time points indicated in the study calendar in Section 10. Samples will be collected and stored by the UAMS Cancer Institute Tissue Bank following established Tissue Bank SOPs. IgM and IgG titers to TACAs will be evaluated by ELISA on TACA adhered to plates and FACS analysis of TACA adhered to liposomes. A positive TACA-directed immune response will be defined as an anti-TACA serum antibody titer of 1:40 for a baseline pre-vaccination titer of 0 or a \geq 4-fold increase over baseline titer > 0 (1, 11). Subjects will be judged to have had an adequate immune response if they have a positive TACA-directed immune response at any one of the first five designated time points following vaccine administration (Weeks 2, 3, 4, 7 and 9). The value of a booster immunization will be determined by anti-TACA IgM and IgG titers obtained from study labs collected on week 21.

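### Pregnancy is tested only before the first dose, so an early, unrecognised pregnancy could be exposed at the Week 7 dose, the Week 19 booster and the skin tests that follow them

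*Combined protocol and SAP*

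**What the plan says.** **Testing.** Criterion 10 in Section 5 excludes pregnant women and specifies that a "negative serum pregnancy test must be done 48 hours prior to receiving the first dose of study drug". In the Study Calendar (Section 10) the pregnancy-test row has two marks: prestudy, and the 48-hour column that stands ahead of Week 1. Footnote 2 says that "a serum pregnancy test must be done at prestudy and within 48 hours prior to dosing. One test may suffice for both". The visit lists in Section 7.d name the test at prestudy and in the entry just before Week 1. No list from Week 1 to Week 24 names it.

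**Contraception.** Criterion 11 reads "Women of childbearing potential must be counseled to use an accepted and effective method of contraception", covering the treatment period and 18 months beyond. The risk table in Section 8.a is firmer, in both the study-vaccine row and the adjuvant row: "Only non-pregnant, non-lactating females may participate" and "The use of contraception during the study and the use of contraception for 18 months post completion of the trial are required".

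**Exposure.** Vaccine is given at Weeks 1, 2, 3, 7 and 19. Section 2 notes that "The immunization at week 19 is considered a booster immunization". Calendar footnote 6 adds that "The DTH skin tests on weeks 5, 9 and 21 will test the DTH response to Mimotope P10s-PADRE", and Section 7.d sets 100 µg intradermally for each of these tests.

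**A pregnancy on study.** Section 8.a lists five conditions for early termination. None names pregnancy, but item (v) leaves room for the investigator's judgement. The dose-limiting criteria (Section 7.f) and the stopping rules (Section 17.b) do not name it either. Section 16.b counts a birth defect as a serious adverse event.

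**The concern.** The protocol keeps pregnant women out because the effects of this type of vaccine on a fetus are not known, and this is its first use in humans. Before the first dose it does not rely on contraception or on history and examination alone; it also asks for a serum test. For a booster given four months later it asks for no test, although the reason for asking has not changed. The Section 8 statement that participants are non-pregnant is therefore verified once, at the start.

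What is at stake is participant protection. A woman who conceived in the weeks before Week 19 could receive the booster, and then the Week 21 skin test, before anyone knew. The same applies to the Week 7 dose and the Week 9 skin test. No endpoint, DLT rule or analysis depends on this.

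**Working it through.** The plan states no figure on this point, so there is none to reproduce. The check is calendar arithmetic plus a search of the text for any repeat test or pregnancy rule.

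**Inputs.** Last required test: within 48 hours before the Week 1 dose (criterion 10; calendar footnote 2). Vaccine at Weeks 1, 2, 3, 7 and 19; P10s-PADRE skin tests at Weeks 5, 9 and 21 (Section 7.d; calendar footnote 6). Visit window: 3 days either way (calendar footnote 7).

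**Age of the test at each later administration** (week minus 1):

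| Week | Given | Age of test (weeks) |
|---|---|---|
| 2 | vaccine | 1 |
| 3 | vaccine | 2 |
| 5 | skin test | 4 |
| 7 | vaccine | 6 |
| 9 | skin test | 8 |
| 19 | vaccine (booster) | 18 |
| 21 | skin test | 20 |

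**With the visit windows.** Week 1 to Week 7 is 6 × 7 = 42 days, so 36 to 48 days. Week 1 to Week 19 is 18 × 7 = 126 days, so 120 to 132 days. The test may precede dose 1 by up to 2 days, which gives a maximum of 50 days at Week 7 and 134 days at Week 19.

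**Contact between doses.** Week 7 to Week 19 is 12 weeks. The calendar shows no study visit between the reading of the Week 9 skin test and Week 19, an interval of about 19 − 9 = 10 weeks.

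**Could the 48-hour rule mean every dose?** Footnote 2 does not say first dose, so the question is fair. Three things settle it: the column appears once, ahead of Week 1; the matching entry in Section 7.d also appears once, in the same place; and criterion 10 specifies the first dose.

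**With a test before Weeks 7 and 19.** The test is at most 2 days old at each of these doses. The skin tests then follow a negative result by about two weeks (9 − 7 = 2; 21 − 19 = 2).

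**Cost.** 2 tests × 18 subjects = 36 assays at most.

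I give no probability of pregnancy. The documents state no conception rate, no contraceptive failure rate and no count of women of childbearing potential.

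**The case against.** The documents agree with one another on a single test, so this is a design choice and not an internal error. Several safeguards also operate after dose 1. Section 8.a requires contraception. History and physical examination are done at Weeks 7, 9, 19 and 21. A known pregnancy can be handled under item (v), and the risk table allows the study drug to be discontinued. The population has stage IV disease, with chemotherapy and anti-estrogen therapy allowed, so few participants may be able to conceive. All of this stands. It narrows the gap to a pregnancy too early to be recognised, which required contraception does not detect and an examination may miss.

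Some stronger readings are tempting, but the documents do not support them:

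- *Contraception is only advised.* Criterion 11 read alone suggests this, but the Section 8.a table makes use a requirement.
- *Every administration after the first dose is unprotected.* At Weeks 2 and 3 the test is only one to two weeks old, about the interval that the proposed change accepts for the Week 9 and Week 21 skin tests. Week 5 lies between, at 4 weeks, and is a skin test rather than a vaccine dose. The point rests on Weeks 7, 9, 19 and 21.
- *Harm to a fetus would go unreported.* Section 16.b makes a birth defect a serious adverse event. What is missing is a rule for the pregnancy itself: stop, report, follow to outcome.
- *Nothing tells participants what to do.* The consent pages are not available for this review, so nothing can be inferred about them.

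**Conclusion.** The point holds as a cheap improvement to participant safety. No pregnancy test is scheduled after the first dose. The last one is about 6 weeks old at the Week 7 dose and about 18 weeks old at the booster, and P10s-PADRE skin tests follow each of those doses. The remaining exposure is that of an early, unrecognised pregnancy. The number of women concerned is probably small; this is a judgement, because eligibility is open from age 18 without a menopausal requirement and the documents give no count. The trial's statistical conclusions are unaffected either way. The finding rests on the protocol text only and makes no claim about consent wording or institutional procedures outside it.

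**What to change.** 1. In the Study Calendar and in the Week 7 and Week 19 visit lists, add: *Serum pregnancy test for women of childbearing potential within 48 hours before vaccination; do not vaccinate unless negative.* Keep the existing test before the first dose.
2. In the Section 8.a conditions, add: *(vi) pregnancy: no further vaccine or P10s-PADRE skin test; report to the Medical Monitor and follow to outcome.*

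The contraception wording can stay. Section 8.a already requires use and counts its 18 months from the end of the trial; restarting that count at the last administration could shorten the period. Taking 18 months as 78 weeks, and assuming that the trial ends for a subject at Week 24, the current text runs to about Week 24 + 78 = 102, against 21 + 78 = 99 from the Week 21 skin test.

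The cost is at most two extra assays per woman of childbearing potential, 36 if all 18 subjects qualify. Study bloods at Weeks 7 and 19 are already taken before the injection, so no extra draw is needed if the result is back in time; otherwise one draw in the preceding 48 hours is needed for each dose. Dose rules, DLT window, endpoints and sample size stay as they are.
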